This application is based on the premise that probationers and parolees must have access to stable, drug free housing to reduce HIV risk, access needed services and avoid rearrests and reincarceration. Drug free housing at the Sober Living Network (SLN) in California will be studied as a way to provide a positive living environment for probationers and parolees. The houses use a sober living house (SLH) model of recovery that includes a communal recovery environment, abstinence from drugs and alcohol, peer support, and encouragement to attend self-help groups such as Alcoholics Anonymous. Preliminary data based on a sample of 300 individuals entering 20 SLHs in California showed resident improvement in a variety of areas, including drug and alcohol use, employment, psychiatric symptoms, and arrests ([name] et al., 2010). Although residents referred from parole and probation systems had substance use reductions that were comparable to voluntary residents, they had had far more problems maintaining employment, higher rates of arrest and incarceration, and lower attendance at self-help groups ([name], et al., 2010). Thirty seven percent had been rearrested at 6 month follow-up and one reason may be that probationers and parolees received only 35% of the services that they felt they needed to succeed. Although over half met DSM IV criteria for methamphetamine dependence during the last year, a very high risk group for HIV, we did not assess HIV outcomes.

The proposed study will improve SLHs for offenders by adding a Motivational Interviewing Case Management (MICM) intervention specifically targeted to the problems presented by each offender. The list of potential problems that MICM can address is extensive: 1) adapting to the SLH environment, 2) complying with parole and probation, 3) finding and maintain work, 4) successfully accessing and maintaining retention in services, 5) addressing HIV risk, testing and treatment, 6) mobilizing personal and informal resources, and 7) managing setbacks (e.g., relapse, loss of housing, loss of work).

Men and women offenders (N=330) entering SLHs will be assigned to a condition consisting of drug free housing and provision of a resources manual where residents can seek help for a variety of problems (a control group) or drug free housing plus the MICM (intervention).

**Aim 1:** To assess HIV testing rates, HIV risk behaviors, and utilization for HIV services at baseline, 6, and 12 months.

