### Primary Outcomes

- 1) Criminal Justice Outcomes are taken from Petersilia (2003) and Petteruti and Walsh (2008) and include: a) Parole/Probation Violations, b) Arrests and c) Days Incarcerated. Arrests will be specified by type of offense and whether the respondent was convicted. Incarceration will be specified as due to arrest for a new offense and due to a technical violation of probation or parole. Data will be self-report but also will be confirmed using publicly available criminal justice records.
- 2) Timeline Follow-Back (TLFB) will be used to record the subject's self-report of alcohol and drug use during each interview period assessed. To maximize recall of alcohol and drug use we will assess 90-day time periods. This instrument has been used extensively in a variety of drug and alcohol studies (Sobel et al., 1996).
- 3) Four scales from the Addiction Severity Index Lite (ASI) (McLellan et al., 1992) will be used as primary outcomes. Alcohol and drug scales will be used to assess alcohol and drug severity, the legal scale will be

uses to assess legal severity and the employment scale will be used to assess employment problems. 3) The Risk Assessment Battery (RAB) (Metzger, et al, 2001) will be used to assess injection and sexual risk behaviors. An additional measure of HIV will include a count of HIV testing overall and the number who are tested for their first time. We will also record self-report of HIV status and current engagement in HIV treatment services (coded yes\no) for those who are positive.

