### Mediators and Moderators of Outcome

1) A short form measuring social support will ask about support from people close to the respondent. 2) We will ask three questions to assess the extent to which individuals in their social network are heavy alcohol and drug users. 3) The Alcoholics Anonymous

Affiliation Scale (AAS) is a nine-item scale that measures the strength of an individual's affiliation with AA and other 12-step groups (Humphreys, Kaskutas & Weisner, 1998). 4) Services Received is a measure from our current study of SLHs that assesses the extent to which participants are involved in a variety of services (e.g., substance abuse, mental health, healthcare, legal and job training) (Hser et al., 1999). 5) Supportive confrontation will be assessed using the Alcohol and Drug Confrontation Scale (ADCS) developed by [name] et al (2006; [name] & Greenfield, 2006). Confrontation is defined as warnings individuals receive about potential consequences of alcohol or drug use from family, friends, peers and professionals. 6) Retention will be assessed as number of continuous days of residence after admission. 7) We will ask a set of questions about the effects of traumatic life events using a PTSD checklist. We will ask about their history of physical and sexual abuse using questions adapted from the National Alcohol Study and the WHO women and violence study. 8) The Alcohol and Drug Consequences Questionnaire (Cunningham, et al., 1997) will be used to assess motivation for change. Two scales assess the consequences and benefits of changing substance use. Consistent with previous studies of SLHs ([name] & Greenfield, 2006) we will also use these items to assess motivation to maintain abstinence.

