Hypotheses H1.1 will be tested in the framework of longitudinal models, as described above. The focus is on treatment condition which, although uniquely assigned to individuals, is implemented at the house level and therefore will be treated as a level 3 variable. This allows for a limited exploratory examination of potential treatment effects with house level characteristics. Interactions of treatment condition with level 2 variables (e.g., gender) can be implemented by simply including treatment as a predictor of the non-randomly varying level 2 coefficient (e.g., gender) of interest. Evidence in favor of the hypotheses will be significant level-3 coefficients (the relevant γ coefficient) for the indicator variables (Z) representing average differences between houses in the rate of change in the outcome over time (i.e., the intercept of the level 2 slope parameter $\lambda_{o,h}$).

Aim 2: *To compare baseline substance use within each study condition with 6- and 12-month substance use.*

H2.1 Residents in each study condition will show significant reductions in drug and alcohol use between baseline and follow-up time points as measured by the Time Line Follow Back (TLFB).

H2.2 Residents in each study condition will show significant reductions in drug and alcohol problems between baseline and follow-up time points as measured by the Addiction Severity Index alcohol and drug scales.

Hypotheses H2.1 and H2.2 will be tested in the framework of longitudinal models, as described above. As a first step, an empty model will be estimated (random intercept and slope but no level 2 (individual) or level 3 (house) covariates) to test whether the variances of the intercept and slope parameters (u and v) are significant. Should significant variation be found, candidate covariates, both at the individual level (level 2) and the house level (level 3), will be considered in separate models and any such covariates will be entered as predictors of both the random intercept and slope.

Aim 3: *To compare outcomes between the two study conditions at baseline, 6, and 12 months.*

H3.1 Residents receiving MMI in addition to drug free housing will have less substance use (TLFB) and lower ASI alcohol and drug severity than the drug free housing and resources condition.

H3.2 Residents receiving MMI in addition to drug free housing will have fewer arrests, fewer days incarcerated and lower ASI legal severity than the drug free housing and resources condition.

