H3.3 Residents receiving MMI in addition to drug free housing will have fewer work problems (ASI Employment scale) and more days worked than the drug free housing and resources condition.

Testing of hypotheses in H3.1 to H3.3 will first be carried out using the same growth curve modeling methods as described for analyses proposed in Aim 1 above.

Aim 4: To assess mediators and moderators of the MMI.

H4.1 Service utilization (Hser et al., 1991) will mediate the relationship between treatment type (drug free housing with vs. without MMI) and outcome (TLFB, ASI Alcohol and Drug scales and criminal justice recidivism).

The best fitting model found from analyses in Aim 2 which include level 3 indicators of treatment condition as predictors of the average random slope (and potentially the random intercept) will serve as the baseline model with which to assess mediation. For treatment predictors of the random slope, overall significance of the 1 degree of freedom test of differences in changes over time between the 32 houses will be assessed using a linear contrast test. Then, time varying covariates (e.g., utilization of services, perceived stress, and negative affect scales) will be entered separately into the model as a level 1 (time within individual) predictor. Then, the same linear contrast test of the level 3 treatment coefficients for the random slope coefficients indicating average differences in change over time between treatment conditions will again be carried out, with reductions in the magnitude of the coefficient estimate and significance of the test indicating the degree to which such variables mediate program differences.

Exploratory Aims:

We will explore a variety of additional outcomes within and between study conditions for which we do not have a priori hypotheses. These will include additional ASI scales (Family, Medical, and Psychiatric) and Housing Status. We will also explore how a variety of covariates are associated with outcome within and across study conditions. Variables assessed will include social support, supportive confrontation, motivation, drug use, age of onset for alcohol and drug use, criminal justice history and status (probation or parole) and gang affiliation. Analytic methods will include first examining univariate distributions and bivariate associations and then entering variables as covariates into the growth curve modeling described above.

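### H4.1 judges mediation by the drop in the treatment coefficient and its significance, with no interval, test or criterion for the indirect effect

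*SAP*

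**What the plan says.** H4.1 is a numbered hypothesis in both documents, separate from the exploratory aims, and the only stated mediation hypothesis. It holds that service utilization mediates the effect of the intervention (MICM in the protocol, MMI in the SAP) on "outcome (TLFB, ASI Alcohol and Drug scales and criminal justice recidivism"). The protocol lists the criminal justice outcomes as "a) Parole/Probation Violations, b) Arrests and c) Days Incarcerated". The mediator is the Services Received measure, which "assesses the extent to which participants are involved in a variety of services" and is scheduled at baseline, 6 months and 1 year.

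The SAP (Analysis of Specific Aims, Aim 4) gives the method in three steps:

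1. Test the treatment difference in change over time with a 1-df contrast on the random slope.
2. Add time-varying covariates, "e.g., utilization of services, perceived stress, and negative affect scales) will be entered separately into the model as a level 1" predictor.
3. Repeat the same contrast, "with reductions in the magnitude of the coefficient estimate and significance of the test indicating the degree to which such variables mediate program differences".

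The protocol states H4.1 without an analysis method. Elsewhere the SAP has a general, conditional multiplicity sentence and names SPSS and MPlus. Neither is tied to an indirect effect.

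**The concern.** The quantity of interest is the indirect effect: MICM changes service use (path a), and service use changes the outcome given MICM (path b). The SAP compares two treatment coefficients and two p-values and does not assess the uncertainty of the difference between them. For H1.1 the SAP says what counts as evidence in favour, namely a significant treatment coefficient on the slope. It has no counterpart for H4.1.

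Two things follow. A drop in the coefficient could be reported as partial mediation with no indication of whether chance alone would produce it. And if the reader falls back on loss of significance, real mediation can be missed, because a treatment effect can stay significant after a genuine part of it has been explained. The dose-response and qualitative analyses bear on mechanism but do not test H4.1.

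**Working it through.** **No stated figure to reproduce.** The documents give no power, threshold or sample size for H4.1. The nearest figure is the main comparison in Power Considerations: 132 per group, d=.35, two-sided α=.05, stated power .82. Recomputed: .35 × √(132/2) = 2.84, and Φ(2.84 − 1.96) = .81, so it agrees to rounding. The check below borrows this effect and sample size.

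**Inputs.** From the SAP: total effect .35, 32 houses, ICC .06, three interviews, about 264 analysable. Assumed: 8 residents per house (32 × 8 = 256), time coded 0/.5/1, variances of .06 (house), .40 (person) and .54 (residual), which sum to 1, slope variances .01 and .05, and **all values of a and b**. There were 2,000 replicates, fitted by generalised least squares.

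**What the drop estimates.** Let c be the treatment-by-time coefficient before adjustment and c′ the coefficient after. In these linear models with complete data, c − c′ = a × b (largest discrepancy below 1e-15). The SAP's quantity is therefore a valid point estimate.

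**How variable it is.** Approximately, SE(ab) = √(a²·SE_b² + b²·SE_a²).

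| a, b | True share ab/.35 | 95% range of drop, % of .35 | Monte Carlo interval excludes 0 | p<.05 lost, of initially significant trials |
|---|---|---|---|---|
| .3, 0 | 0 | −7 to +7 | 2% | 1.6% |
| .5, 0 | 0 | −10 to +11 | 5% | 2.8% |
| 1, 0 | 0 | −20 to +22 | 6% | 6.7% |
| 0, .1 | 0 | −8 to +8 | 3% | 1.7% |
| 0, .3 | 0 | −24 to +23 | 6% | 4.5% |
| 0, .5 | 0 | −38 to +38 | 6% | 7.5% |
| .3, .2 | .06/.35 = 17% | 1 to 35 | 59% | 20-23% |
| .5, .3 | .15/.35 = 43% | 19 to 71 | 95-96% | 54-60% |

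In the six no-mediation rows the last column also requires the coefficient to drop. In those rows the coefficient drops in 50-52% of trials. A house-level bootstrap excludes zero in 4-8% of no-mediation trials, and in 63% and 95% of trials in the last two rows. Ranges in the last two rows come from repeated runs.

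**Hand check of the ranges.** The (1, 0) row has half-width (.076 + .070)/2 = .073, so SE_b ≈ .073/1.96 = .037. The (0, .5) row has half-width .1325, so SE_a ≈ .1325/(1.96 × .5) = .135. For (.5, .3): SE = √(.25 × .037² + .09 × .135²) = .0445, and .15 ± 1.96 × .0445 = .063 to .237, or 18% to 68% of .35. The simulated range is 19% to 71%.

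**House count.** The protocol plans 70 houses. With 70 × 4 residents (1,000 replicates) the coefficient drops in 48-53% of no-mediation trials and the Monte Carlo interval excludes zero in 3-6%. With real mediation it excludes zero in 63% (.3, .2) and 98% (.5, .3).

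**If recidivism is analysed as binary.** Take a control risk of .37, from the protocol's preliminary study ("Thirty seven percent had been rearrested at 6 month follow-up"), and an assumed MICM risk of .25. With a=0 and b=.3 or .5 per SD on the logit scale, the treatment coefficient rises by 1.9% or 5.1% although nothing is mediated. With a=.3, b=.5 the drop is 21%, the product of paths 27%, and the risk-scale share 23%. On that scale the drop is no longer the indirect effect.

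**The case against.** **The rule has two parts, and the second is not lax.** The SAP looks at the coefficient and at its significance. With no mediation, loss of p<.05 with a dropping coefficient occurs in about 2-7% of initially significant trials, similar to the proposed interval. This stands: the fault of that reading is poor sensitivity. The SAP speaks only of a reduction in significance, so loss of p<.05 is itself one interpretation.

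**The wording is descriptive.** The SAP speaks of a degree of mediation, not a verdict. But H4.1 asserts that services will mediate, and a degree reported without its uncertainty cannot support that.

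**Stronger readings that a reader might infer, and that do not hold:**

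- *The rule has a 50% false-positive rate.* Any estimate centred on zero falls on one side about half the time, and the SAP does not say that any drop establishes mediation.
- *A 20% drop always fits both chance and mediation.* A chance drop of at least 20% occurs in 0-0.1% of no-mediation trials at (.3, 0), (.5, 0) and (0, .1), and in about 3-16% at the three larger settings. No document supports any path size.
- *The SAP uses same-visit services, so reverse causation inflates the result.* It says time-varying and level 1, not concurrent or lagged. The direction is also open. If better outcomes raise service use (reverse path .1-.3, a=.5, no mediation), the coefficient drops in 98-99% of trials; if worse outcomes prompt services, it dropped in none.
- *Arrest will be a binary outcome.* The SAP names arrests and incarceration as growth-curve outcomes and specifies no logit model.
- *The starting model is wrong.* Aim 4 begins from "The best fitting model found from analyses in Aim 2 which include level 3 indicators of treatment condition". Aim 2 allows house-level covariates, and Aim 1 makes treatment one ("The focus is on treatment condition which, although uniquely assigned to individuals, is implemented at the house level"), so the pointer can be read consistently. The stress and affect scales are only examples and do not bear on H4.1.

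**Conclusion.** The gap stands, and it is one of specification. H4.1 is judged from a point estimate with no interval, test or criterion for the indirect effect. This rests on the text and not on the simulation.

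Its size depends on assumed paths. With no mediation, 95% of chance drops lie within about ±7% to nearly ±40% of a .35 SD effect. Where mediation is real, loss of p<.05 signals it in roughly a fifth of initially significant trials (a=.3, b=.2) or just over half (a=.5, b=.3). A Monte Carlo interval excludes zero in 59% and 95-96% of all trials; the denominators differ, but the gap is wide.

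The treatment comparisons under Aims 1-3 do not use this rule and are unaffected. The point should be addressed before H4.1 is analysed, but it does not threaten the trial's main conclusions.

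**What to change.** In the Aim 4 section of the SAP:

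- For each H4.1 outcome, estimate the indirect effect of MICM through Services Received in the three-level model: treatment to change in services, and services to outcome given treatment. Give it a Monte Carlo or house-level bootstrap interval.
- Call a result consistent with mediation only if the interval excludes zero in the hypothesised direction. Do not interpret a drop in the coefficient, or a change in its p-value, alone.
- Apply the SAP's multiplicity procedure across the H4.1 outcomes. The simulated detection rates above are for unadjusted 95% intervals and would be lower after adjustment.
- State whether services enter concurrently or lagged, and that concurrent data do not establish temporal order.
- If a recidivism outcome is analysed as a count or binary variable, use a suitable link, and do not take the difference in logit coefficients as the indirect effect.

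The cost is SAP wording and modest extra analysis in MPlus, which is already named; no new data are needed. The interval guards against chance only. Under the positive reverse path above (a=.5, no mediation) it excludes zero in 76-99% of trials, so the temporal-order caveat must accompany any positive result. Clarifying the Aim 2 pointer, trimming the example covariates and adding a lagged analysis are optional.

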### **Summary of Inclusion/Exclusion Criteria**

We plan to recruit only offenders who are HIV+ or at high risk for HIV. Inclusion criteria will require at least one of the following: HIV+, MSM, history of injection drug use, history of sex work, and past month unprotected anal or vaginal sex with more than one partner. All potential participants will be recruited from a pool of individuals who have a history of substance dependence and criminal justice involvement, factors known to be associated with HIV infection and risk (Belenko, 2006). Over half of our potential sample will have a history of methamphetamine dependence, another high risk factor (Center for Disease Control, 2007). Offenders must be able to speak English and those who show evidence of a serious mental health disorder that would hinder their ability to provide informed consent will be excluded. Study therapists will conduct these assessments when necessary and make a determination. In addition, to be included in the study residents must agree to be randomly assigned to one of the 2 study conditions and provide some contact information that can be used to locate them for follow-up interviews.

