A second exploratory aim is to conduct 30 qualitative interviews (15 in each condition) to identify general and intervention specific factors that were perceived to affect outcomes and ways to improve the two active interventions. An initial coding list will include specific codes suggested by characteristics of the intervention. For example, codes for the SLH alone condition might include things like “helped me increase support to not use alcohol or drugs,” and “helped me avoid exposure to alcohol and drugs.” For MMI, codes might include “made suggestions for services” and “helped me prepare for living at the SLH.” For meditation, codes might include things like “helped me relax” and “increased positive feelings about myself.” Using line-by-line coding, themes and excerpts of text will be highlighted as quotations that exemplify salient resident attitudes and beliefs. Excerpts will be printed out, and each analyst will group the excerpts into thematic categories. The extent of agreement between the analysts’ initial coding of the data will be assessed. Each analyst will define the working themes and through discussion select a final set. Data will be entered into the qualitative software program, N Vivo. The research team will use the constant comparison method and analytic memoing to identify patterns, create themes or categories, and develop theoretical insights (Strauss & Corbin, 1990).

Power Considerations

Given our sample of 165 in each of the 2 study conditions and our expectation that we will contact 80% of the sample at 12 months we should have 132 per group and a total N of 264 available for analysis for at least two time points. For tests of equality of paired differences in means for outcomes between the final interview and baseline between the two study conditions, power to detect small-to-medium effect sizes ($d=.35$) would be .82 in 2-sided tests with $\alpha=.05$.

Similar power is available for tests of equality of proportions (Cohen, 1988).

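### The SAP's blanket statement of similar power for proportions does not hold for HIV treatment engagement, which is recorded only in HIV-positive participants

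*SAP*

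**What the plan says.** The Power Considerations section of the SAP starts from the full sample: "Given our sample of 165 in each of the 2 study conditions", with the expectation that "we will contact 80% of the sample at 12 months", so that "we should have 132 per group and a total N of 264 available for analysis". For a two-sided 5% comparison of mean change between conditions it states that "power to detect small-to-medium effect sizes ($d=.35$) would be .82". The next sentence extends this to binary outcomes: "Similar power is available for tests of equality of proportions". It gives no proportions, no denominators and no exceptions. The section ends by calling power more than adequate in general terms.

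H1.1, in both documents, predicts three things under the intervention: more HIV testing, more use of HIV services and less HIV risk behaviour. The protocol's Primary Outcomes section describes the HIV-specific service item as "current engagement in HIV treatment services (coded yes\no) for those who are positive". The table under Measures lists HIV treatment in the primary outcome block.

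The protocol's Summary of Inclusion/Exclusion Criteria shows that HIV-positive participants are a subset by design: "Inclusion criteria will require at least one of the following: HIV+, MSM, history of injection drug use, history of sex work", with recent unprotected sex with more than one partner as a further route. Neither document gives the expected HIV-positive share or a separate power figure for treatment engagement.

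**The concern.** A power figure belongs to a denominator. The only power statement for proportions rests on 132 per arm, but one yes/no item in the primary block cannot have that denominator unless nearly everyone enrolled is HIV-positive. A reader of the SAP would take the statement to cover this item, because nothing excludes it. A non-significant difference in treatment engagement could then be read as evidence that the intervention does not help, when the comparison had little chance of detecting an effect of the size the SAP uses.

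**Working it through.** **Inputs.** From SAP, Power Considerations: 165 per arm, 80% followed at 12 months, 165 × .80 = 132 per arm, effect .35, two-sided alpha .05, stated power .82. The HIV-positive share is not in the documents, so a range is assumed. The share and the retention rate are taken to be the same in both arms and in HIV-positive and other participants.

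**Step 1: reproduce the SAP's figure.** With n per arm and standardised effect d, power ≈ Φ(d√(n/2) − 1.96). For n = 132 and d = .35: .35 × √66 = 2.843; 2.843 − 1.96 = .883; Φ(.883) = .81. A noncentral t calculation with 262 degrees of freedom also gives .81. This agrees with the stated .82 to within about .01.

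**Step 2: the same for proportions in the full sample.** With Cohen's arcsine effect h = .35 the formula is identical, so power is again .81. A direct two-proportion calculation for pairs with h = .35 gives the same to two decimals (for example, 50% v 67.1% gives .81, and 20% v 35.5% gives .81). As arithmetic on 132 per arm, ignoring clustering, the sentence is right.

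**Step 3: change the denominator.** Put n = 132 × share into the same formula, adding the small opposite tail Φ(−h√(n/2) − 1.96), which matters only at the lowest shares.

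| Assumed HIV-positive share | n per arm | h√(n/2) | Approximate power at h = .35 |
|---|---|---|---|
| 5% | 6.6 | .636 | .10 |
| 10% | 13.2 | .899 | .15 |
| 20% | 26.4 | 1.272 | .25 |
| 50% | 66 | 2.011 | .52 |
| 100% | 132 | 2.843 | .81 |

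At about 7 per arm the normal approximation is rough, so the first row is only an order of magnitude.

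**Step 4: the share needed for .80.** n = 2 × ((1.960 + .842)/.35)² = 128.1 per arm, and 128.1/132 = .97. Power falls below .80 at any share under about 97%.

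**Step 5: the difference that could be detected.** For 80% power, h = 2.80/√(n/2). At a 20% share this is 2.80/3.63 = .77, or engagement rising from 50% to about 85%. At a 50% share it is .49, or 50% to about 73%.

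**Step 6: clustering.** Houses are randomised, and Steps 1 to 5 ignore this, as the SAP's simple calculation does. Later in the same section the SAP reduces 132 to 132/(1 + 32 × .06) = 45. Taking that 45 as printed, power at h = .35 even for an outcome measured in everyone is Φ(.35 × √22.5 − 1.96) = Φ(−.30) = .38. If the design effect is instead built on 264/32 = 8.25 completers per house, it is 1 + 7.25 × .06 = 1.435, n is 92 and power is .66. Both are well below .82.

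**The case against.** The strongest reply is that the quoted sentence contains no miscalculation. It is a general remark about 132 per arm, names no outcome, and reproduces at .81. That stands: the defect is a missing exception, not wrong arithmetic. But it is the SAP's only power statement for proportions, and a yes/no item in the primary block falls within it unless excluded.

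Second, H1.1 does not define HIV services, and equating them with treatment engagement is an inference. That also stands. The protocol's Services Received measure covers healthcare among other services and is not limited to HIV-positive participants. However, it is a general measure listed with mediators and moderators. Besides testing, treatment engagement is the only HIV-specific service measure described. The point is therefore about that item and does not show that every possible reading of HIV service use is underpowered.

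Third, the size of the shortfall rests on an assumed share. True, and the range is wide, but the direction does not depend on the choice below about 97%.

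Fourth, H1.1 is to be tested in three-level longitudinal models, not by a single 12-month comparison. So the figures describe the SAP's own simple calculation with a corrected denominator, not the power of the planned model. At a 20% share there would be about 264 × .20 = 53 HIV-positive completers, fewer than two per house over the SAP's 32 houses, so little support for the larger model should be expected.

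**Conclusion.** The point holds for HIV treatment engagement. At h = .35, two-sided alpha .05, 12-month completers and no clustering, approximate power is .10 to .52 for HIV-positive shares of 5% to 50%, against the .82 that the SAP says is similarly available for proportions. It reaches .80 only at about 97% or more. The share is an assumption throughout, because the documents give none.

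Three stronger readings are not supported:

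- A reader might infer that the claim fails at every share below 100%. It does not: at 97% and above, power is still about .80. The alternative entry routes do make so high a share unlikely.
- A reader might infer that a weak comparison on this item undermines H1.1 as a whole, or that the item decides it. The documents contain no rule for combining the three parts of H1.1, and no power figure is given for this item specifically.
- A reader might infer that, once this item is set aside, the statement is sound for all other proportions. It is right only before clustering; the SAP's own effective n of 45 per arm gives about .38.

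**What to change.** In SAP, Power Considerations:

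1. Limit the statement on proportions to binary outcomes measured in all participants, and mark it as before allowance for house clustering. Alongside it, give the figure implied by the SAP's own effective n of 45 per arm (about .38 at h = .35).
2. State that the power claim does not cover HIV treatment engagement, because that item is recorded only for HIV-positive participants and their expected number is not specified.
3. State that treatment engagement will be reported in the HIV-positive subset as an estimated difference with a confidence interval and the number per arm, so that a non-significant result is not read as evidence of no effect. Self-reported HIV status is already collected at baseline, so these numbers can be given.

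The cost is SAP wording only, with no change to design, sample size or data collection. The downside is that a stated power becomes less favourable.
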